3.2 Randomisation and blinding

3.2.1 Randomisation

This is a double-blind randomised study. At Visit 1 (Baseline) all eligible subjects will be randomised via the IRT to one of the four treatment regimens (BGS649 0.1 mg, 0.3 mg, and 1.0 mg and matched placebo) in a 1:1:1:1 ratio. After the interim analysis (see Section 8.8.1.2), if one or more of the BGS649 study arms is discontinued by the DMC, the dosing for that arm(s) will be stopped and no further randomisation to that arm will be performed. The remaining subjects will be randomised into the remaining active arms versus placebo (ineffective or unsafe dose will not continue). The IRT will assign a medication number to the subject, which will be used to link the subject to a treatment regimen and will specify a unique medication number on the label of investigational treatment to be dispensed to the subject.

3.2.2 Blinding

Subjects, investigational staff, persons performing the assessments and data analysts (with the exception of unblinded DMC staff/members) will remain blind to the identity of the treatments [REDACTED] from the time of randomisation until completion of the randomisation phase. In order to maintain the blind described above, testosterone measurements will be blinded to site and sponsor staff and monitoring will be performed by an independent unblinded physician.

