Reference Therapy, Dose and Duration of Administration: 
Those subjects randomised to the placebo arm will be administered matching placebo capsules that are indistinguishable to the test product in appearance and taste but contain no active ingredient.
 
All doses should be taken orally by the subject, with water, on a weekly basis (± 1 day from the time schedule of regular planned dose) at approximately the same time of the day.
		
Duration of Treatment: 
All subjects will be treated with BGS649 or matched placebo for a maximum of 24 weekly doses (which provides 24 weeks therapeutic coverage due to long half-life of BGS649). Some subjects who complete 24 weeks of treatment will be invited to participate in a 6-month blinded safety extension study (Protocol MBGS206). An interim analysis will be performed once approximately 100 of overall planned enrolled subjects have completed the Week 4 visit and any doses of BGS649 that did not lead to normalisation of testosterone or were considered unsafe will be identified and the dose arm terminated.
		

Name of Sponsor/Company: Mereo BioPharma 2 Ltd	Individual Study Table Referring to Part of the Dossier:	(For National Authority Use Only)
Name of Product: BGS649		
Name of Active Ingredient: 4,4'-[fluoro-(1-H-1,2,4-triazol-1-yl)methylene]bisbenzotrile	Volume: Page:	

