9 INVESTIGATIONAL PLAN

9.1 Overall Study Design and Plan

9.1.1 Description

This is a phase IIb, multicentre, double-blind, randomised, placebo-controlled parallel-group 36-week study evaluating safety and efficacy of BGS649 in male obese subjects with HH. The study will have three phases:

1. A **Screening Phase** lasting up to 28 days (Screen Visit 1, Screen Visit 2), including Day -28 to Day -1
2. A **Randomisation Phase** including the Baseline visit (Day 1) and the treatment period Day 1 to Visit 8 (Week 24)
3. A **Safety Follow-Up Phase** to Visit 11 (Week 36, follow up [FU]). Visits 9 and 10 are telephone assessments.

Study participation will comprise up to 2 Screening Visits, 8 visits during the treatment period up to Week 24 (End of Treatment [EOT]), FU Visits 9, 10 (telephone assessment) and 11 (at Weeks 28, 32 and 36 respectively) for safety performed to 12 weeks after Visit 8 (EOT) (see schedule of assessments, [Table 9–1](#)). PK in seminal fluid will be performed at Visit 8. A minimum of 25 subjects per treatment arm will be invited to participate in a 6-month extension study (Protocol MBGS206), starting at Visit 8 (EOT). This transfer will be handled by the interactive response technology (IRT) and the blind will be maintained. Subjects participating in the 6-month extension will have their last study visit at Visit 8 (EOT) and will not participate in Visits 9, 10, and 11. The study design is summarised in [Figure 9–1](#). The end of the study will be the last visit of the last subject.

Subjects that agree to participate in the trial (informed consent form [ICF] process completed; subject has signed and dated ICF) will be screened (Screening Phase) and assessed against inclusion/exclusion criteria. Symptoms of androgen deficiency will be assessed based on the questionnaire provided (see [Section 12.8](#)) and all positive symptoms will be entered in the electronic case report form (eCRF).

Testosterone levels to be taken before 11 am. If there is evidence that screening was failed due to a sample inadvertently being taken after this time, technical error (for example due to failure to meet storage conditions defined in laboratory manual) or clinically discrepant results ($>100\text{ng/dl}$ difference between tests with one test being $\leq 200\text{ng/dl}$), a retest is allowed in discussion with the Medical Monitor.

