10.2.4 Blinding and Randomisation of Study Treatment(s)

At Visit 1 (Baseline) all eligible subjects will be randomised via the IRT to one of the four treatment regimens [REDACTED] in a 1:1:1:1 ratio. After the interim analysis (see [Section 13.6](#)), if one or more of the BGS649 study arms is discontinued by the DMC, the dosing for that arm(s) will be stopped and no further randomisation to that arm will be performed. The remaining subjects will be randomised in a 1:1:1 ratio into remaining active arms: [REDACTED]

[REDACTED] The investigator or his/her delegate will contact the IRT after confirming that the subject fulfils all the inclusion/exclusion criteria. The IRT will assign a medication number to the subject, which will be used to link the subject to a treatment regimen and will specify a unique medication number on the label of investigational treatment to be dispensed to the subject. The randomisation number will not be communicated to the caller.

The randomisation numbers will be generated using the following procedure to ensure that treatment assignment is unbiased and concealed from subjects and investigator staff. A subject randomisation list will be produced by ICON Biostatistics using a validated system that automates the random assignment of subject numbers to randomisation numbers. These randomisation numbers are linked to the different treatment regimens, which in turn are linked to medication numbers. A separate medication list will be produced using a validated system that automates the random assignment of medication numbers to packs containing the investigational drug.

Subjects, investigational staff, persons performing the assessments and data analysts (other than those described below) will remain blind to the identity of the treatments [REDACTED] from the time of randomisation until database lock. In order to maintain the blind described above, testosterone measurements will be blinded to site and sponsor staff and monitoring will be performed by an independent unblinded physician. The interim analysis will be performed by an independent unblinded committee (see [Section 16.3](#)).

The blind will be maintained using the following methods:

1. Randomisation data will be kept strictly confidential until the time of blinding, and will not be accessible to anyone involved in the study

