13.7 Interim Clinical Study Report

The primary efficacy analysis and study unblinding will be performed when all data up to Visit 8 (Week 24) has been collected. Given the study has been powered at Week 24 and there will not be multiple comparisons, there is no requirement to adjust the Type I error rate.

An interim Clinical Study report (CSR) will be prepared based upon the results of this analysis.

The safety data collected during the off treatment 12 week follow-up will be separately analysed and published in the full CSR.

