3.2.3 Unblinding

Upon completion of the randomization phase (final Week 24 or EOT data collected for the final subject) the blind will be broken and the primary efficacy analysis completed. The 12 week, off treatment, follow up safety data will be analyzed separately.

Emergency treatment code breaks should only be undertaken when it is essential to treat the subject safely and efficaciously. Emergency code breaks are performed using the IRT.

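### The Week 24 unblinding is not limited to an analysis team, so men still in follow-up or in the blinded extension could have their remaining data collected with allocation known.

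*SAP*

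**What the plan says.** SAP 3.2.2 names the blinded groups: "Subjects, investigational staff, persons performing the assessments and data analysts (with the exception of unblinded DMC staff/members) will remain blind" to treatment identity, and this holds "from the time of randomisation until completion of the randomisation phase". SAP 3.2.3 fixes the end point: "Upon completion of the randomization phase (final Week 24 or EOT data collected for the final subject) the blind will be broken", followed by the primary efficacy analysis. Protocol 13.7 gives the same timing: "The primary efficacy analysis and study unblinding will be performed when all data up to Visit 8 (Week 24) has been collected".

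Protocol 10.2.4 gives a different end point for the same groups, "from the time of randomisation until database lock", without saying which lock is meant.

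On the extension, the protocol synopsis (Duration of Treatment) speaks of a "6-month blinded safety extension study (Protocol MBGS206". Protocol 9.1.1 says of the move at Visit 8: "This transfer will be handled by the interactive response technology (IRT) and the blind will be maintained". A footnote to the SAP study flow chart repeats this.

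The amendment summary gives the reason for analysing at Week 24: ineffective MBGS206 doses can then be stopped, and men can be kept from moving into an ineffective arm.

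**The concern.** Analysing at Week 24 is a deliberate and reasonable choice. It requires an analysis team to hold the codes and some sponsor staff to see results by arm. It does not require subjects, investigators or assessors to learn individual allocation, yet SAP 3.2.2 ends the blind for all of these groups at the same moment.

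Some of the data still to come involve judgement:

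- Adverse events are assessed at Visits 9, 10 and 11, the first two by telephone (Protocol Table 9–1), and are collected to 90 days after the last dose (Protocol 12.1.2).
- The investigator rates intensity (Protocol 12.1.2) and causality (Protocol 12.1.3).
- Visit 11 also collects patient-reported outcomes, grip strength and actigraphy.
- SAP 8.7.1 tabulates adverse events for the follow-up period and overall, by treatment regimen.

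If allocation becomes known, men followed up before and after the unblinding date are assessed under different conditions but reported in the same tables. For transferred men, the blind promised for the extension would depend on rules found in neither document.

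**Working it through.** No sample-size calculation is involved. The check is a timeline, followed by a comparison of the blinding statements.

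**1. The plan's own duration.** Screening is Day -28 to Day -1 (4 weeks), treatment runs to Week 24, and follow-up lasts 12 weeks (SAP 3.1). 4 + 24 + 12 = 40 weeks, which matches the maximum in SAP 3.3.

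**2. Adverse event window for a man who completes treatment.** There are 24 weekly doses starting on Day 1, so the last falls on Day 1 + 7 × 23 = Day 162. The window closes 90 days later: 162 + 90 = Day 252, and 252 / 7 = Week 36. It therefore spans the follow-up period.

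**3. What remains for the last man at unblinding.** Week 24 falls on Day 1 + 7 × 24 = Day 169. If the codes are opened then, he has 36 − 24 = 12 weeks of follow-up left if he does not transfer, with 252 − 169 = 83 days of the adverse event window. If he transfers, the whole 6-month extension lies ahead. The trigger is the collection of his data, so the actual date may be slightly later.

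**4. Who else is exposed.** Unblinding happens once, at a date U. Each man has his own Visit 8 date, V.

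| Man | Exposed if | Time still to run at U |
|---|---|---|
| Did not transfer | U − V is under 12 weeks | 12 weeks − (U − V) |
| Did not transfer | U − V is over 12 weeks: not exposed | none |
| Entered MBGS206 | U − V is under about 6 months | about 6 months − (U − V) |
| Entered MBGS206 | U − V is over about 6 months: not exposed | none, if the extension ran to plan |

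**5. Can the number be worked out?** No. It depends on how Visit 8 dates are spread and on how many men transfer, and neither is given. The documents give only a minimum invitation of 25 per arm, or 4 × 25 = 100 men (SAP 8.8.1.2 records that no arm was dropped at the interim). That counts invitations. It is neither the number who enter nor the number still in the extension at U.

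**6. The statements side by side.**

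| Source | When the blind ends |
|---|---|
| SAP 3.2.2 and 3.2.3 | Final subject's Week 24 or end-of-treatment data, for all named groups |
| Protocol 13.7 and SAP 8.9 | All data up to Visit 8 collected |
| Protocol 10.2.4 | Database lock, not specified |
| Protocol synopsis and 9.1.1; SAP flow chart footnote | Extension blinded; blind kept at transfer |

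The first two rows agree. The third fits them if a Week 24 lock is meant and contradicts them if the final lock is meant. The fourth is in tension with the first two, because nothing in either document keeps subjects, sites or assessors blind after the Week 24 unblinding.

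**The case against.** The strongest reply is that the consequence is small and the exposure unproven. Several parts of it stand.

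- The primary endpoint is a central-laboratory testosterone value collected before the codes are opened. It is not affected.
- Follow-up is off treatment and analysed separately. SAP 8.7.1 splits adverse events by period, so treatment-period events remain separable, and comparisons of adverse events are descriptive. Under SAP 7.1.4.1, events after entry to the extension are not counted in this study.
- Overlap with a running extension is intended, as the amendment summary shows.

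The reply also guards against four stronger readings that a reader might infer and the documents do not support.

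- *That all extension data would be unblinded.* Men transfer one by one, and data gathered before the single unblinding date are blinded. Only the tail is exposed.
- *That 100 or more men are affected.* That is the minimum number invited.
- *That the SAP departs from the protocol.* Protocol 13.7 sets the same timing, and the lock in Protocol 10.2.4 is unspecified.
- *That codes will be sent to sites.* The text ends the guarantee of blinding and states no restriction. Disclosure is therefore permitted, not shown to happen.

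Finally, MBGS206 has its own protocol, which is not available here and may contain its own safeguards. That would resolve the extension part by cross-reference, but men in MBGS205 follow-up would remain uncovered.

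The reply does not remove the main point. SAP 3.2.2 expressly names subjects, site staff and assessors among those whose blind ends. That is a stated rule, not a missing detail.

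**Conclusion.** The point holds as a correction that should be made, not as a threat to the primary result. SAP 3.2.2 and 3.2.3, in line with Protocol 13.7, end the blind for people who may still be reporting or assessing data, and neither document limits the unblinding to those who need it.

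The exposure is confined to men still in follow-up (Visit 8 in the preceding 12 weeks, not transferred) or still in MBGS206 (entered in roughly the preceding 6 months) at the single unblinding date. For one man it is at most 12 weeks of follow-up or about 6 months of extension. The number of men cannot be derived.

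The data at risk are follow-up adverse event reports and causality ratings, Visit 11 patient-reported outcomes and the remaining extension data. The conclusion assumes that no separate unblinding plan or MBGS206 rule already restricts access; neither document cites one for the Week 24 unblinding.

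**What to change.** In SAP 3.2.2–3.2.3 and Protocol 10.2.4 and 13.7:

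- State who is unblinded at Week 24: a named analysis team, and the sponsor staff who need arm-level results for extension decisions.
- Keep subjects, site staff and assessors blind to individual allocation, and withhold subject-level results from sites, until the last MBGS205 follow-up visit. For transferred men, continue for as long as the MBGS206 protocol requires, by cross-reference.
- Say which database lock Protocol 10.2.4 means, and reconcile it with Protocol 13.7 and SAP 3.2.2–3.2.3.

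The cost is wording in both documents and an access list. The timing and content of the Week 24 analysis do not change, and the arm-level results needed for decisions on MBGS206 remain available.

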3.2.3 Unblinding

Upon completion of the randomization phase (final Week 24 or EOT data collected for the final subject) the blind will be broken and the primary efficacy analysis completed. The 12 week, off treatment, follow up safety data will be analyzed separately.

Emergency treatment code breaks should only be undertaken when it is essential to treat the subject safely and efficaciously. Emergency code breaks are performed using the IRT.

3.3 Study treatments and assessments

During the 24 week randomization phase, subjects in the BGS649 groups and the matching placebo group will take the required dose weekly (± 1 day from the time schedule of regular planned dose) with water. Subjects will receive three capsules per dose to deliver a total of [REDACTED] [REDACTED] and two indistinguishable placebo capsules) [REDACTED] [REDACTED] or placebo [REDACTED] [REDACTED]

Dose changes are not permitted during the randomization phase.

The maximum study duration from screening to end of the safety follow-up period is 40 weeks.

A detailed description of procedures and assessments to be conducted during this study is summarised in the Schedule of Study Assessments in Table 1 below.

Table 1: Schedule of Study Assessments

Visit	Screening Phase		Randomisation Phase (Treatment Period)								Follow-Up ¹		
	Screening (D -28 to D -1)	Screen Visit 1	1 (Baseline)	2	3	4	5	6	7	8 (EOT)	9	10	11 (FU)
Week/Day	Screen Visit 2 (Visit 1 + 3-7 days)	Screen Visit 1	D 1	D 8 (±1 D)	W4 (±2 D)	W8 (±2 D)	W12 (±2 D)	W16 (±2D)	W20 (±2 D)	W24 (±2 D)	W28 ² (±2 D)	W32 ² (±2 D)	W36 (±2 D)
Written informed consent	X												
Demographics	X												
Medical/surgical history	X												
Inclusion/exclusion criteria	X												
Androgen deficiency symptom checklist	X												
Randomisation			X										
Full general physical exam and prostate exam and breast exam	X						X			X			
Limited physical exam³	X		X	X	X	X	X	X	X	X	X	X	X
Vital signs ⁴ ; height (Visit 1 only)	X		X	X	X	X	X	X	X	X	X	X	X
12-Lead ECG	X		X										
Specialised chemistry: morning cortisol, TSH, FT4, prolactin, iron, transferrin ⁵	X		X										
25 hydroxy vitamin D			X										
Clinical laboratory tests: haematology, blood chemistry, eGFR by Cockcroft-Gault formula, dipstick urinalysis ⁶ and PSA ⁷	X		X	X	X	X	X	X	X	X	X	X	X
Cardiometabolic parameters 1: HbA1c, fasting lipids (total cholesterol, LDL, HDL, triglycerides) ⁷	X				X			X		X			X
Cardiometabolic parameters 2: Fasting glucose and insulin, hs-CRP, HOMA-IR			X				X			X			X
Bone turnover markers^{7,8}													
Sex hormones 1: testosterone (total), oestradiol (total), LH	X ^{9,11}	X ^{9,10,11}	X ¹¹	X ¹¹	X ¹¹	X ¹¹	X ¹¹	X ¹¹	X ¹¹	X ¹¹	X ¹¹	X ¹¹	X ¹¹
Bioavailable testosterone, SHBG			X ¹¹	X ¹¹	X ¹¹	X ¹¹	X ¹¹	X ¹¹	X ¹¹	X ¹¹	X ¹¹	X ¹¹	X ¹¹
Sex hormones 2: FSH			X	X	X	X	X	X	X	X	X	X	X

Visit	Screening Phase	Randomisation Phase (Treatment Period)										Follow-Up ¹	
		1 (Baseline)	2	3	4	5	6	7	8 (EOT)	9	10	11 (FU)	
Week/Day	Screening (D -28 to D -1) Screen Visit 1 + Screen Visit 2 (Visit 1 + 3-7 days)	D 1	D 8 (±1 D)	W4 (±2 D)	W8 (±2 D)	W12 (±2 D)	W16 (±2D)	W20 (±2 D)	W24 (±2 D)	W28 ² (±2 D)	W32 ² (±2 D)	W36 (±2 D)	
DHT, inhibin A and B		X				X			X			X	
Semen quality analysis ¹²		X				X							
Semen PK samples ¹³								X					
Plasma PK samples ¹⁴					X			X					
Hip and waist measurement		X				X			X				
Body composition using bioimpedance ¹⁵ (by impedance)		X				X			X				
Actigraphy ¹⁶		X				X			X			X	
Grip strength		X		X		X			X			X	
PROs: IIEF, BFI, PROMIS SexFS, PROMIS Fatigue Short Form, PGI-S		X		X		X			X			X	
PROs: SF-36		X				X			X			X	
DEXA	X ¹⁸											X ¹⁸	
Study treatment													
Study drug dispensation													
Study drug accountability										X	X	X	
AE assessment ¹⁹		X				X			X	X	X	X	
Concomitant medication	X	X				X			X	X	X	X	

- 1 A minimum of 25 subjects per treatment arm will be invited to participate in a 6-month extension study (Protocol MBGS206), starting at Visit 8 (EOT). Subjects participating in the 6-month extension will have their last study visit at Visit 8 (EOT)
- 2 Telephone Assessment Visit only
- 3 Limited physical examination (cardiovascular system and lower extremities oedema)
- 4 Vital signs assessment will include the measurement of SBP, DBP, pulse, oral temperature and body weight
- 5 Fasting transferrin
- 6 A microscopic examination including RBC and WBC will be performed only when dipstick evaluation is positive for WBC and/or blood
- 7 All blood samples are to be collected after 8 hours fasting, after ECG and vital sign measurements
- 8 Bone turnover markers include CTx1, osteocalcin, bone alkaline phosphatase and P1NP
- 9 At Screening serum total testosterone concentration must be < 300 ng/dL (10.4 nmol/L) based on two morning samples, taken before 11 am at least 3 days apart. Laboratory parameters from screening visit 1 do not need to be received before screening visit 2 is take place

- 10 Oestradiol and LH will not be measured at this visit
- 11 Samples to be collected in the morning before 11 am pre-dose
- 12 Semen quality analysis will include semen volume, sperm count, concentration, motility and morphology. Sample collection is not required to be the same day as the assessment visit. Therefore sample collection is allowed within +/-48 hours the scheduled visit for Baseline and attendance Visits during the treatment phase
- 13 Semen samples for seminal fluid PK is not required to be the same day as the assessment visit. Therefore semen PK collection is allowed +/- 48 hours around the attendance visits
- 14 Samples will be taken at pre-dose and 1h post-dose for sparse plasma PK sampling at Visit 5 (week 12). Investigators should ensure that Visit 5 where plasma PK is measured coincides with the study drug dosing day. At EOT Visit 8 (Week 24), PK will be taken only once together with other laboratory assessments taken at that visit.
- 15 Subjects should come well hydrated, drinking water the night before and the morning before the impedance measurements
- 16 Activity wrist monitors will be worn by subjects for 7 continuous days after Baseline visit and visit 5 and 7 continuous days before Visits 8 and 11, so that the monitors can be collected at Visit 8 from subjects transferring to the extension study and at Visit 11 from subjects completing FU visit.
- 17 Screening PRO's should be performed no more than 7 days before dosing and may be performed outside of the Screen Visit 2 to meet this timing if required
- 18 Screening DEXA scan will be performed during screening and up to Day 8 after randomisation. The End of treatment DEXA will be performed only in a case patient reached minimum visit 5(w12) and it can be performed within 14 days before EOT to accommodate scheduling
- 19 The administration of the study drug (BGS649/placebo) will be performed at the study site on Week 12 to allow measurement of PK at pre-dose and 1h post-dose
- 20 SAEs collected from signature of informed consent and AEs, AESIs collected from randomization.

